# 8.1 Statistical methods for the analysis of the primary endpoints: comparison with external study control groups

#### 8.1.1 Type I error for the Primary Endpoints

The overall one-sided type I error for the study was set at 2.5%. One of the two planned interim efficacy analysis was conducted in March 2015 after 56.4% of subjects had completed 6 months follow up. The O'Brien-Fleming one-sided alpha level for the final analysis (i.e. the stage 2 alpha level) is 2.409%.

Final testing for the three analyses of the primary endpoint will follow an alpha-exhaustive, fallback procedure [8].

An alpha level of 2% will be used with OS, 0.309% will be used with CS and the remaining 0.1% will be used for the analysis of OS in the pre-specified subgroups. The testing will proceed as presented in Figure 3 (below); in this way, the family-wise error rate is preserved at 2.409% for the primary endpoints.

The additional pre-specified subgroup analyses will be conducted in order, at the same alpha level as for the MGMT methylated subgroup, as follows.

[figure not shown]
- 2. Extent of resection: Minimal residual disease
- 3. Age < 65
- MGMT unmethylated
- 5. Extent of resection: Significant residual disease
- 6. Age ≥ 65

#### Success of the study

The significance of each of the endpoints will be tested via one-sided upper confidence limits for the hazard ratios. Figure 3 shows the possible outcomes of the study.

Figure 3: Decision tree for study success

Where 
$$r = \frac{\alpha_2}{(\alpha_1 + \alpha_2)} = \frac{0.3}{2.3} = 0.13$$

Page 32 of 57

#### 8.1.2 Threshold and methods for conditional survival

The median survival time in months, M, for all subjects randomized to receive DCVax®-L will be estimated via the Kaplan-Meier estimate of the survival function. This value will be used as the threshold for the conditional survival endpoint.

The proportional hazards assumption will be assumed to hold for CS for the DCVax®-L group and the external controls and the Cox model will be used to compare these groups. The assumption will be checked graphically.

#### 8.1.3 External studies in newly diagnosed GBM

A systematic literature review has been conducted by independent experts to identify appropriate studies in newly diagnosed GBM to provide the external controls. This selection of studies has subsequently been reviewed by independent key opinion leaders in the field who were not involved in conducting the Trial, and has received their support. The five studies shown in Table 3 [6, 13-16], which were conducted in similar populations as in the current Phase III study, each with a control arm treated with the standard radiotherapy and temozolomide regimen, will be included. It is possible that additional studies may be added, e.g. with the goal to provide a larger population of patients with long (e.g.  $\geq$  4 years) follow-up times. In addition, a MAIC will be undertaken to ensure matching of the Trial subjects and the external controls.

It is recognized that each of these studies had unique inclusion and exclusion criteria, and that no single study can provide a perfectly matched control population. Nevertheless, the distribution of known prognostic factors between the enrolled patient populations reveal that these populations were similar in composition, and in fact the study outcomes are also remarkably similar: These five studies selected by the independent expert review provide 1,366 patients for the combined control group in total.

Median overall survival for these 1,366 patients is 16.5 months, with a 95% confidence interval of 16.0 to 17.5 months, demonstrating that outcome in this disease is highly consistent and predictable.

The Gilbert et al. (2014) study randomized patients 3 weeks prior to completion of chemoradiation therapy, and if that study is excluded from the analyses the outcomes of the control subjects are as follows: n=1,057; mOS=16.8 months (95% CI: 16.1-17.7 months).

Page 33 of 57 Confidential

Table 3: Studies selected providing comparable control arms

[figure not shown]
Lead	Year	Journal	CONT	ROL GROUP		
author			Treatment	N	Median OS (months)	OS Kaplan-Meier curves available for subgroups
Gilbert	2013	JCO	XRT + temozolomide	411	16.6	MGMT methylated (N = 122), unmethylated (N = 254)
Stupp	2017	JAMA	XRT + temozolomide	229	16.0	Age < 65y (N = 184), Age ≥ 65 y (N = 45),  MGMT methylated (N = 77),  unmethylated (N = 95)
Weller	2017	Lancet oncology	XRT + temozolomide	374	17.4	Minimal residual disease N = 210), Significant residual disease (N = 163)
Wen	2019	CCR	XRT + temozolomide	43	15.0	None
Gilbert*	2014*	NEJM	XRT + temozolomide	309	16.1	None

\*Gilbert 2014 randomized study subjects at an earlier timepoint then the other studies, and all analyses will be conducted both including and excluding this study.

Median overall survival and a 95% confidence interval for the control arm in each of the five studies is shown in Figure 4, demonstrating that the control arms had similar median overall survival.

Figure 4: Overall survival comparisons for selected studies: control arms

Study authors of the external studies selected by independent expert review will be contacted to request access to their individual patient data (IPD), for their control groups. Where possible, the original data will be used.

Where the original data are not available, the published Kaplan-Meier survival curves will be digitised and, along with the number at risk at each time (where available), will be used to reconstruct the survival and censoring times (IPD) of the control arm subjects in the external studies using the Guyot method [17]. Figure 5 shows the re-constructed Kaplan-Meier survival curves for the control arms for the five example studies, constructed by digitization and overlaid.

[figure not shown]

Figure 5: Kaplan-Meier overall survival curves for selected studies

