#### 1.2.1 Primary endpoint: OS compared with external controls – 3 analyses

**Analysis #1: Overall survival in the whole patient population**: This analysis will evaluate the overall survival curves and median survival for all of the patients in the Trial (both ITT and PP populations). This analysis will compare the survival times of the 232 patients initially randomized to DCVax®-L to the selected external controls. The comparisons will include the following:

- an overall comparison of the 232 patients to all external control patients, pooled;
- a matching-adjusted indirect comparison (MAIC) that takes into account the distribution of prognostic factors between the 232-patient DCVax®-L trial population and the external controls, pooled;
- a MAIC of the 232 patients to the control patients of each individual external control trial.

All comparisons will include an overall curve comparison, as well as comparisons of survival percentages at certain time points (so-called milestone analyses).

Analysis #2: Conditional survival -- the "long tail": This analysis will evaluate specifically the "long tail" of survival in patients treated with DCVax®-L in this Trial. With immunotherapies, one of the features most focused upon and considered most important clinically is their capability to deliver greatly extended survival in a percentage of patients. This analysis will apply an established statistical methodology – conditional survival – to evaluate the survival tail in this Trial separately from the larger picture. This methodology will evaluate all of the survival data relating to patients who survived beyond a specified time threshold. (This time threshold is the "condition" or trigger of the analysis). By analysing all of the data from the time threshold onwards, this methodology evaluates the whole survival tail and provides a more complete and representative assessment than a landmark analysis which would only evaluate the status of the survival tail at a specific time point.

**Analysis #3: Survival in pre-specified sub-groups:** It has become well recognized that GBM patients may be categorized into distinct sub-groups based upon certain patient characteristics and/or tumor characteristics, and these distinct sub-groups have materially different survival with GBM. Such

SAP Version: 1.0

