# 8.1.5 Comparison of treatments: if only published data are available for external studies

#### Primary analysis: simple proportional hazards models, external studies pooled

Where the original data are not available, the primary analysis will be a comparison between the reconstructed individual patient survival data reconstructed (by digitizing the published KM curves), for all subjects, pooled across the external studies, with the 232 subjects randomized to DCVax®-L. This analysis will include the published data from all of the studies independently selected to serve as controls for the Trial, regardless of whether they have been included with their IPD in the analysis above. For the MGMT methylated subgroup comparison, the individual patient data will be reconstructed for the external studies where the Kaplan-Meier curves are available for the subgroup (199 subjects in total for the 5 studies identified).

For the other subgroup comparisons, the individual patient data will be reconstructed for the external studies where the Kaplan-Meier curves are available for the subgroup. The following subgroups would be possible for the 5 studies identified to date, with the stated numbers of subjects (available from the external control populations) in each (see Table 3). Other subgroups may also be available if further studies are identified in the independent literature review. The subgroups will be analyzed in the following order:

•	MGMT promoter methylated	N = 199
•	Minimal residual disease	N = 210
•	Age < 65:	N = 184
•	MGMT unmethylated:	N = 349
•	Age >= 65:	N = 45
•	Significant residual disease:	N = 163

Overall survival

• The hazard ratio will be constructed for OS.

Survival conditional on survival to M months

The hazard ratio will be constructed for CS (conditional on survival to M months).

Overall survival for subgroups

- The hazard ratio will be constructed for OS for the MGMT methylated.
- The hazard ratio will be constructed for OS for other subgroups similarly where possible.

The confidence intervals for the hazard ratios will be constructed in line with the significance levels shown in Figure 3.

Job Number: 1555 Customer Reference: Study ID: 020221 SAP Version: 1.0

Kaplan-Meier estimates of the survival functions for the DCVax®-L population and the pooled comparator population will be plotted and estimates of survival (with 95% confidence intervals) at 6, 12, 18, 24, 30, 36, 42, 48, 54 and 60 months will be calculated.

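### The list of external control studies is not closed before unblinding, and the pool that decides the primary test is not named outright, so the stated 2% level for OS is not guaranteed

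*Combined protocol and SAP*

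**What the plan says.** SAP 8.1.3 commits to the five control arms in Table 3: "These five studies selected by the independent expert review provide 1,366 patients for the combined control group in total". The next step is left open: "It is possible that additional studies may be added, e.g. with the goal to provide a larger population of patients with long" follow-up, with at least 4 years given as an example. Section 8.1.3 also describes the five as examples, and 8.1.5 describes them as those identified so far.

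The primary comparison is described in 1.2.1 as "an overall comparison of the 232 patients to all external control patients, pooled". Section 8.1.5 likewise takes in the published data of every study independently selected as a control.

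One of the five studies (309 controls) randomised 3 weeks before chemoradiation ended. The note to Table 3 says that "all analyses will be conducted both including and excluding this study". Section 8.1.3 gives the results for both pools: "Median overall survival for these 1,366 patients is 16.5 months, with a 95% confidence interval of 16.0 to 17.5 months", and without that study "n=1,057; mOS=16.8 months (95% CI: 16.1-17.7 months").

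The alpha is split in 8.1.1: "An alpha level of 2% will be used with OS, 0.309% will be used with CS and the remaining 0.1% will be used" for the pre-specified subgroups. The same section says that the family-wise rate is held at 2.409%. The Executive summary dates the SAP before data lock and unblinding.

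**The concern.** The external controls replace the randomised control in the test that decides the trial. The stated error rates hold only if the comparator is fixed independently of the DCVax-L outcome. The five control arms' results are already known (Figures 4 and 5). If a further study can join the pool at any time, and the text does not say which of two pre-planned runs decides, then nothing written prevents the comparator from being settled once both sides are visible. The stated reason for adding studies, more long-term follow-up, bears most directly on the conditional-survival test.

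At stake are the 2% level for OS and the 2.409% claim. So is the credibility of a comparator whose main defence is that it was chosen independently.

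**Working it through.** **1. The plan's own figures.** Table 3: 411 + 229 + 374 + 43 + 309 = 1,366; less 309 = 1,057. Both match 8.1.3. An exponential mixture of the Table 3 medians gives 16.54 months for five studies (stated 16.5) and 16.67 for four (stated 16.8). The alpha split is 2 + 0.309 + 0.1 = 2.409%, as stated.

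**2. What closes the list?** Section 8.1.3 permits additions, and 8.1.5 puts each independently selected study in the primary pool. No sentence gives a closing date, and none restricts a later study to sensitivity use.

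**3. Assumptions for sizing.** The documents do not give death counts or the number and size of added studies, so these are illustrative:
- DCVax-L deaths: 200 of 232.
- Controls: 84% dead, so 0.84 × 1,366 = 1,147 deaths (five studies) and 0.84 × 1,057 = 888 (four).
- Each optional added study: 300 patients, 252 deaths.
- No treatment effect and no between-study heterogeneity.
- The most favourable permitted result is the one used.

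**4. Formulae.** SE of the log hazard ratio = √(1/d_T + 1/d_C), where d_T and d_C are deaths in the DCVax-L arm and the control pool. The one-sided 2% critical value is z = 2.054. Two tests on nested control pools with the same DCVax-L arm have a correlation equal to the smaller SE divided by the larger.

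- Five studies: √(1/200 + 1/1,147) = 0.0766.
- Four studies: √(1/200 + 1/888) = 0.0783, about 2% larger.
- Five plus one added: d_C = 0.84 × 1,666 = 1,399; √(1/200 + 1/1,399) = 0.0756.

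**5. Chance that at least one permitted version passes at z = 2.054.** The two-version cases follow from the bivariate normal: correlation 0.0766/0.0783 = 0.979 gives 2.4%, and 0.0756/0.0766 = 0.987 gives 2.3%. The others were simulated over every permitted pool.

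| Freedom left open | Pools to choose from | One-sided level |
|---|---|---|
| None (pool fixed) | 1 | 2.0% |
| With/without runs only | 2 | about 2.4% |
| One optional study, five-study pool kept | 2 | about 2.3% |
| Three optional studies, five-study pool kept | 8 | about 2.9% |
| With/without, plus one optional study | 4 | about 2.8% |
| With/without, plus three optional studies | 16 | about 3.5% |

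If 70–90% of DCVax-L patients and 60–90% of controls have died, the with/without figure stays within 2.35–2.46%.

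**6. Effect on the control median.** With the same exponential mixture, one added study of 500 controls with a median anywhere in the Table 3 range (15.0 to 17.4 months) would put the pooled median between 16.1 and 16.8 months. With 1,000 controls the range is 15.9 to 16.9.

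**The case against.** **The timing is inferred.** The SAP predates data lock and unblinding, and the five named studies are a floor. A reader might infer that the comparator will be changed once the DCVax-L results are known. The documents say nothing of the kind. What stands is that nothing in the available text rules it out.

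**There are entry criteria.** SAP 1.1 lists comparable populations, trial period, extent of resection and standard chemoradiation. Section 8.1.5 ties further studies to the independent literature review. The search report in Appendix A is attached separately and is not available here, so it would be wrong to say that no entry rule exists. Entry criteria alone would still not close the list or settle the role of a later study.

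**The with/without rule is pre-specified.** Both control medians are disclosed, and 1.2.1 and 8.1.5 point to the full pool as primary. This stands: the gap here is a missing label, and the 2.4% applies only if the choice really is free.

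**The subgroup list.** Section 8.1.5 says "Other subgroups may also be available if further studies are identified in the independent literature review". A reader might take this to mean that the alpha-carrying hierarchy can grow. No sentence says that new subgroups join the six listed in 8.1.1.

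**Larger inflation.** Rates of roughly 3.3% to 7.3% can be produced by giving the added studies, and only those, a between-study SD of 0.10 to 0.15 on the log hazard, on top of the with/without choice. The documents give no such SD. If the same SD is applied to every control arm, a frozen five-study pool already runs at about 4.2% (SD 0.10) or 7.0% (SD 0.15). Most of that is a pooling-model problem, which closing the list would not cure.

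**Conclusion.** The point holds as a gap in pre-specification. The SAP expressly permits additions, its primary analysis would absorb them, and nothing in the available text closes the list or limits later studies to sensitivity use. Which of the two planned runs feeds Figure 3 is implied but not stated.

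The consequence is that 2% for OS, and hence 2.409% overall, is not guaranteed. On the assumptions above, inflation is modest: 2.3% to 2.9% from optional additions alone, 2.4% from the with/without choice alone, and 2.8% to 3.5% from both. These figures are for deliberate use of the most favourable version, and they take the controls as exchangeable with the trial arm. Bias from the non-randomised comparison is separate and not included.

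It would go too far to say that the 2%, 0.309% and 0.1% levels are void. Only the OS test was sized; the conditional-survival and subgroup levels were not computed.

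**What to change.** In SAP 8.1.3, before data lock and unblinding:

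1. Close the list of control studies, with a dated record.
2. State that any study added later enters only a labelled sensitivity analysis and cannot alter the Figure 3 decision or the six-subgroup hierarchy.
3. Name one pool as deciding and label the other as sensitivity.

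Either pool would close the gap. The five-study pool (n = 1,366) is what 1.2.1 and 8.1.5 imply. The four-study pool (n = 1,057) is open to the sponsor if comparable randomisation timing is preferred; it costs about 2% in standard error and moves the stated control median from 16.5 to 16.8 months. The documents do not settle which is less biased. An earlier clock lengthens control survival, while randomising before a post-chemoradiation progression screen shortens it.

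The cost is a few sentences of SAP text. The downside is that studies found later, including any with longer follow-up, cannot contribute to the confirmatory test.

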#### 8.1.4 Comparison of treatments: if original data are available for external studies

For each study where the original IPD are available, a Cox proportional hazards regression will be conducted comparing the pooled control groups from the external studies with DCVax®-L. Covariates will be included as available. A hazard ratio and 95% confidence interval will be determined.

Kaplan-Meier estimates of the survival functions for the DCVax®-L population and the comparator population will be plotted and estimates of survival (with 95% confidence intervals) at 6, 12, 18, 24, 30, 36, 42, 48, 54 and 60 months will be calculated. Conditional survival and subgroup comparisons will be estimated similarly.

In addition, if original IPD from the comparator studies are available, a matched case-control comparison based on known prognostic factors may be feasible and may be conducted as a sensitivity analysis.

# 8.1.5 Comparison of treatments: if only published data are available for external studies

#### Primary analysis: simple proportional hazards models, external studies pooled

Where the original data are not available, the primary analysis will be a comparison between the reconstructed individual patient survival data reconstructed (by digitizing the published KM curves), for all subjects, pooled across the external studies, with the 232 subjects randomized to DCVax®-L. This analysis will include the published data from all of the studies independently selected to serve as controls for the Trial, regardless of whether they have been included with their IPD in the analysis above. For the MGMT methylated subgroup comparison, the individual patient data will be reconstructed for the external studies where the Kaplan-Meier curves are available for the subgroup (199 subjects in total for the 5 studies identified).

For the other subgroup comparisons, the individual patient data will be reconstructed for the external studies where the Kaplan-Meier curves are available for the subgroup. The following subgroups would be possible for the 5 studies identified to date, with the stated numbers of subjects (available from the external control populations) in each (see Table 3). Other subgroups may also be available if further studies are identified in the independent literature review. The subgroups will be analyzed in the following order:

•	MGMT promoter methylated	N = 199
•	Minimal residual disease	N = 210
•	Age < 65:	N = 184
•	MGMT unmethylated:	N = 349
•	Age >= 65:	N = 45
•	Significant residual disease:	N = 163

Overall survival

• The hazard ratio will be constructed for OS.

Survival conditional on survival to M months

The hazard ratio will be constructed for CS (conditional on survival to M months).

Overall survival for subgroups

- The hazard ratio will be constructed for OS for the MGMT methylated.
- The hazard ratio will be constructed for OS for other subgroups similarly where possible.

The confidence intervals for the hazard ratios will be constructed in line with the significance levels shown in Figure 3.

Job Number: 1555 Customer Reference: Study ID: 020221 SAP Version: 1.0

Kaplan-Meier estimates of the survival functions for the DCVax®-L population and the pooled comparator population will be plotted and estimates of survival (with 95% confidence intervals) at 6, 12, 18, 24, 30, 36, 42, 48, 54 and 60 months will be calculated.

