OS ITT & PP procedure for log rank test  Sensitivity analyses: Internal to Study 020221  OS ITT & PP Cox PH Hazard ratio; landmarks  PFS ITT & PP Hazard ratio; landmarks  OS ITT & PP biomarker subgroup8 Hazard ratio; landmarks  PFS ITT & PP biomarker subgroup Hazard ratio; landmarks  Exploratory: Internal to Study 020221	cPFS 	ITT & PP	Cox PH	Hazard ratio; landmarks	5			
OS ITT & PP log rank test  Sensitivity analyses: Internal to Study 020221  OS ITT & PP Cox PH Hazard ratio; landmarks  PFS ITT & PP Hazard ratio; landmarks  OS ITT & PP biomarker subgroup  Hazard ratio; landmarks  PFS ITT & PP biomarker subgroup Hazard ratio; landmarks  Exploratory: Internal to Study 020221	PFS	ITT & PP	Karrison	Hazard ratio; landmarks	5			
OS ITT & PP Cox PH Hazard ratio; landmarks PFS ITT & PP Hazard ratio; landmarks OS ITT & PP biomarker subgroup  Hazard ratio; landmarks PFS ITT & PP biomarker subgroup Hazard ratio; landmarks  Exploratory: Internal to Study 020221	OS	ITT & PP		Hazard ratio; landmarks	5			
PFS ITT & PP Hazard ratio; landmarks OS ITT & PP biomarker subgroup  Hazard ratio; landmarks PFS ITT & PP biomarker subgroup Hazard ratio; landmarks  Exploratory: Internal to Study 020221	Sensitivity	analyses: Internal to Study 020221						
OS ITT & PP biomarker subgroup  Hazard ratio; landmarks PFS ITT & PP biomarker subgroup Hazard ratio; landmarks  Exploratory: Internal to Study 020221	OS	ITT & PP	Cox PH	Hazard ratio; landmarks	5			
PFS ITT & PP biomarker subgroup Hazard ratio; landmarks  Exploratory: Internal to Study 020221	PFS	ITT & PP		Hazard ratio; landmarks	5			
Exploratory: Internal to Study 020221	OS	ITT & PP biomarker subgroup 		Hazard ratio; landmarks	5			
	PFS	ITT & PP biomarker subgroup		Hazard ratio; landmarks	5			
TTP  ITT Hazard ratio; landmarks	Exploratory: Internal to Study 020221							
	TTP 	ITT		Hazard ratio; landmarks	5			

 $^{1}$   $\alpha$  5% 2 sided overall; accounting for interim analysis, final analysis to be conducted at  $\alpha$  2.409% 1 sided

<sup>2 Subjects randomized to DCVax®-L

<sup>3 Control arms from studies in newly diagnosed GBM identified in systematic literature review by independent experts, confirmed with independent neuro-oncology experts and further matched through MAIC

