#### 3.1.1 Overall survival

For the Primary Endpoint, analyses #1 (ITT Population) and #3 (Pre-Specified Sub-Groups), OS will be calculated from the date of randomization to the date of death due to any cause. If a subject is not known to have died at the date of database lock, that subject will be censored at the date the subject was last known to be alive. For these Primary Endpoint analyses, OS for subjects randomized to DCVax®-L will be compared to closely matched, independently determined external controls.

For Secondary Endpoint #1 (Post-Progression OS), OS will be calculated from the date of progression to the date of death due to any cause for subjects originally randomized to placebo who received DCVax®-L after crossover. If a subject is not known to have died at the date of database lock, then the death for that subject will be censored at the date that the subject was last known to be alive. For these Post-Progression OS analyses, the subjects who received DCVax®-L after crossover will be compared to matched external controls obtained from trials in recurrent GBM.

For Secondary Endpoint #4 (OS in the ITT population), OS will be calculated from the date of randomization to the date of death due to any cause or date the subject was last known to be alive in the same manner as for the Primary Endpoint analysis #1, except that the OS for subjects randomized to DCVax®-L will be compared to Within-Study controls (i.e. subjects randomized to placebo).

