#### Sensitivity analysis 1: Matching-adjusted indirect comparison (MAIC), external studies pooled

A matching-adjusted indirect comparison (MAIC) will be used to compare the treatment groups. The MAIC technique is explained in detail in Appendix D.

Overall survival

The MAIC will be adjusted for the following characteristics.

Table 4: Characteristics to be matched via MAIC: selected studies

Characteristic	Number of studies	Cate	gories
MGMT methylation status	5	methylated	unmethylated
Performance status (KPS)	4	< 90%	>= 90%
Surgical status	4	Complete resection / minimal residual disease	Incomplete resection / significant residual disease
Sex	5	M	F
Race	4	White	Non-white
Age	5	Continuous	

The numbers of subjects in each subgroup will be calculated for each study where the information is available. For factors where the information is available for all external studies, the overall proportions across all 1,366 subjects can then be calculated. For factors recorded in only four out of the five studies, the proportion of subjects in those studies will be applied to all the 1,366 subjects for the purposes of matching.

For the pooled published studies, the reconstructed IPD will be compared to the weighted data resulting from matching (see Appendix D) from the DCVax®-L subjects. A Cox proportional hazards model will be used to estimate the treatment effect in the form of a hazard ratio.

Kaplan-Meier estimates of the survival functions for the weighted DCVax®-L population and the comparator population will be plotted and estimates of survival to 6, 12, 18, 24, 30, 36, 42, 48, 54 and 60 months will be calculated (with 95% confidence intervals).

Survival conditional on survival to M months

Conditional survival analysis using MAIC weights will not be feasible using published data, but will be conducted if original individual patient data are available.

Overall survival for subgroups

It may not be feasible to analyse survival in subgroups using the MAIC approach if the proportions of subjects with the relevant characteristics are not known for the subgroups unless the original data is available from comparator studies. If such data is available, this analysis will be conducted.

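### The 2% overall survival test is an unadjusted comparison, although the SAP describes the external controls as matched through MAIC; the deciding test and the control set should each be named once before unblinding

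*Combined protocol and SAP*

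**What the plan says.** **The deciding test.** SAP 8.1.1 allots 2% one-sided to overall survival (OS), 0.309% to conditional survival (CS) and 0.1% to subgroups. The success paragraph after it judges significance by one-sided upper confidence limits for the hazard ratios (HRs). Section 8.1.5, under "Primary analysis: simple proportional hazards models, external studies pooled", sets the 232 patients randomized to DCVax-L against digitised control data from all selected studies, and sets its intervals at the Figure 3 levels. It lists no covariates or weights. The pooled MAIC and the study-by-study MAICs follow as sensitivity analyses 1 and 2.

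**The description of the controls.** Table 2 footnote 3 calls the controls for the primary endpoint "confirmed with independent neuro-oncology experts and further matched through MAIC", and 3.1.2 uses the same words for CS. Section 3.1.1 says "OS for subjects randomized to DCVax®-L will be compared to closely matched, independently determined external controls", without naming MAIC. The executive summary also calls the control group closely matched.

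**Competing candidates for the alpha.** If individual patient data (IPD) are obtained, 8.1.4 and Table 2 footnote 4 add whatever covariates are available. Section 8.1.5 still runs on every study regardless. Sensitivity analysis 2 ends with a meta-analysis whose upper limit is to be set at the alpha of 8.1.1. Section 1.2.1 lists the pooled comparison and the MAICs together under Analysis #1.

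**Conditional survival.** Against 3.1.2, sensitivity analysis 1 states: "Conditional survival analysis using MAIC weights will not be feasible using published data".

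**The control set.** Section 8.1.3 names five studies and adds: "It is possible that additional studies may be added". For the 309-patient arm randomized earlier than the others, the Table 3 footnote says "all analyses will be conducted both including and excluding this study".

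**The concern.** The external controls replace a randomized comparison. Without randomization, any net prognostic difference between the 232 patients and the pooled controls passes straight into the HR. The SAP answers this with matching, but the test that spends the alpha does not use it. A reader of Table 2 would believe that the primary result is adjusted; a programmer following 8.1.5 would produce one that is not.

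The same uncertainty extends to which analysis decides and which controls it uses. With up to three hazard ratios that could claim the alpha, two versions of the control set and no date after which it is closed, the primary result is not uniquely defined in advance.

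**Working it through.** **1. The plan's own figures.** The split adds up: 2 + 0.309 + 0.1 = 2.409%. Section 8.1.1 records: "One of the two planned interim efficacy analysis was conducted in March 2015 after 56.4% of subjects had completed 6 months follow up". Taking 0.564 as the information fraction, Lan-DeMets O'Brien-Fleming spending at one-sided 2.5% gives a final level of 2.409%, as stated. Table 3 adds up: 411 + 229 + 374 + 43 + 309 = 1,366, and 1,366 − 309 = 1,057. The SAP gives no power or event count for the external comparison.

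**2. Precision of the unadjusted test.** SE(log HR) = √(1/d₁ + 1/d₀), with d₁ = 232f and d₀ = 1,366f. The death fraction f is not in the documents; I assume 0.70–0.90 in both groups.

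- f = 0.70: √(1/162.4 + 1/956.2) = 0.085
- f = 0.90: √(1/208.8 + 1/1,229.4) = 0.075

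With z = 2.054 at 2% one-sided, the largest passing HR is exp(−2.054 × SE), or 0.84–0.86.

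**3. False positives with no treatment effect.** If case mix alone produces HR b, the rejection rate is 1 − Φ(2.054 + ln b / SE). The values of b are assumptions.

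| Case-mix HR b | f = 0.70 | f = 0.90 |
|---|---|---|
| 1.05 (against DCVax-L) | 0.4% | 0.3% |
| 1.00 | 2.0% | 2.0% |
| 0.95 | 7.4% | 8.6% |
| 0.90 | 20.8% | 25.9% |

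**4. Is b of this order plausible?** On a log-linear approximation, b = exp(Δp × ln HR of the factor). A 10-point difference in one factor with an assumed prognostic HR of 0.6 gives exp(0.10 × ln 0.6) = 0.95; 20 points gives 0.90. For scale, Table 3 reports MGMT methylation in 122/(122 + 254) = 32% of one control arm and 77/(77 + 95) = 45% of another, a gap of 12 points before rounding. This shows that arms described as similar can differ by that much. It does not show how the DCVax-L arm differs from them.

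**5. Two control sets.** With equal death fractions, the correlation of the two test statistics is √[(1/232 + 1/1,366)/(1/232 + 1/1,057)] = 0.98. Taking the better of two tests at 2% gives about 2.4%. The effect of studies added later cannot be bounded from the documents.

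**6. Price of adjustment.** Appendix D weights the DCVax-L patients, so the effective sample size (ESS) reduces d₁. I assume 50–90% of 232, that is 116–209. Then SE = √(1/(d₁ × ESS fraction) + 1/d₀). The SAP's OS effect (section 1.3.2) is HR 17/25.3 = 0.672.

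| | Unadjusted | Pooled MAIC |
|---|---|---|
| SE(log HR) | 0.075–0.085 | 0.078–0.116 |
| Largest passing HR | 0.84–0.86 | 0.79–0.85 |
| Power at HR 0.672 | 99.6–99.9% | 92–99.9% |
| Power at HR 0.80 | 72–82% | 45–79% |

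**7. Conditional survival.** Baseline weights need only the control averages already used for OS, so a weighted comparison of survivors at M can be computed. It does not match the survivors. Illustration, all assumed: 40% carry a factor with HR 0.5, balanced at baseline, and treatment HR is 0.672. M is the treated median, where 0.4x + 0.6x² = 0.5 with x = exp(−0.336H), so x = 0.638 and H = 1.335. The favourable share at M is 0.4 × 0.638/0.5 = 51% among treated patients and 0.4 × 0.513/(0.4 × 0.513 + 0.6 × 0.263) = 57% among controls.

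**The case against.** The strongest reply is that adjustment is planned. Six matching factors, the weighting method, the robust standard error and the reporting of effective sample size are all specified. Digitised curves carry no covariates, so their absence from 8.1.5 reflects the data, and 8.1.4 adds covariates if IPD arrive. This stands as far as it goes: a reader who infers that the SAP has no adjustment would be wrong. But MAIC needs covariates only for the treated patients and averages for the controls, so the data limit does not explain why the weighted analysis is secondary. The covariates in 8.1.4 are also not listed.

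A reader might also infer that the comparator can be chosen after unblinding. The documents do not say that. Five studies are named for inclusion, the pooled analysis uses all selected studies, and sensitivity analysis 1 matches to 1,366 patients, so five looks like the default. What is missing is a closing date and a statement of which version is primary. The medians of 16.5 and 16.8 months barely differ, and choosing between the two sets costs little. Appendix A, the literature-search report, is not available here and may bear on selection.

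Others might infer that the four-study version must be primary because the fifth study randomized before chemoradiation ended, whereas this trial took only patients without progression afterwards. The documents do not say whether the other four studies excluded progressors, so they do not settle that choice.

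Finally, MAIC is no cure for unmeasured differences. Appendix D itself concedes that it rests on an unverifiable assumption. IDH status and progression-free status after chemoradiation are not in Table 4. This limit stands and belongs in the SAP.

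**Conclusion.** The point holds as a contradiction in the text with a material consequence. The analysis at the 2% level is unadjusted, while Table 2 footnote 3 and 3.1.2 describe matching through MAIC. The analysis that carries the alpha is not uniquely identified. The CS statements in 3.1.2 and 8.1.5 conflict when only published data are available. The control set is not closed.

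The missing adjustment is the main problem: about 7–9% false positives at a case-mix HR of 0.95 and 21–26% at 0.90, against a nominal 2%. These figures rest on assumed death fractions of 70–90%, assumed case-mix HRs and no treatment effect. They do not show that the comparison favours DCVax-L: imbalance the other way makes the test conservative, and the documents do not give the direction. The two control sets alone move 2.0% only to about 2.4%.

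It would go too far to say that 3.1.1 promises MAIC (it says only closely matched), or that a baseline-weighted CS analysis delivers matched survivors.

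**What to change.** 1. **Name one OS test.** Make the pooled MAIC of 8.1.5 (sensitivity analysis 1), with the robust standard error of Appendix D, the single 2% test. Report the unadjusted Cox model as sensitivity. State that any IPD-adjusted analysis under 8.1.4, and the MAIC meta-analysis, are supportive and carry no alpha.
2. **Close the control set before unblinding.** Name either the version with or the version without the 309-patient arm as primary. The other version and any later study enter sensitivity analyses only.
3. **Reconcile CS.** Either apply the baseline MAIC weights with both groups restricted to survivors at M, stating that this balances the groups at randomization and not among survivors at M; or delete the MAIC statement from 3.1.2 and call the CS test unadjusted.
4. **State the limit.** Say that MAIC does not correct for factors outside Table 4, such as IDH status and progression-free status after chemoradiation.

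The OS change promotes an analysis already specified and needs no new data. The cost is effective sample size: under the ESS assumed above, power at HR 0.672 stays at 92% or more, but at HR 0.80 it falls from 72–82% to 45–79%.
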